Study Protocol and Statistical Analysis Plan
Using hydroxychloroquine to treat nonalcoholic steatohepatitis

Study Title : Using hydroxychloroquine to treat nonalcoholic steatohepatitis

Study Principal Investigator (PI) : [name]., Ph.D.

Study Director : [name]

Objective : To examine whether hydroxychloroquine can treat nonalcoholic steatohepatitis effectively.

Abstract :

[figure not shown]
Nonalcoholic steatohepatitis (NASH) is a serious type of nonalcoholic fatty liver disease (NAFLD), which is characterized by lobular inflammation and apoptosis resulting from hepatic steatosis in the absence of excessive alcohol consumption[1]. If NASH are not controlled well, it will advance to liver fibrosis, cirrhosis[1], and even hepatocellular carcinoma[2]. However, there is no approved treatments currently.

According to guidance of American Association for the Study of Liver Diseases (AASLD) and a few studies, vitamin E and pioglitazone are two potential pharmacologic therapies for NASH. They have some therapeutic effects; however, they also have some safety concerns[3]. Therefore, those two drugs have not been widely used in clinical practices. In addition to vitamin E and pioglitazone, many drugs are being tested in clinical trials. However, promising results have not been revealed yet.

[figure not shown]
Recent clinical and experimental data suggested that hydroxychloroquine (HCQ) might improve metabolic profiles in patients or animals with obesity-related metabolic disorders[4, 5]. HCQ might also relieve liver inflammation in experimental animals with steatohepatitis[5]. As an inhibitor of endocytosis and autophagy with therapeutic effects in autoimmune disorders[6], it is reasonable to speculate that HCQ might also relieve liver inflammation in patients with steatohepatitis. Therefore, HCQ has been anecdotally prescribed to patients with steatohepatitis in our clinic. Excitingly, almost all those with HCQ treatment had immediate reduction of their liver enzyme levels, indicating instant relief of their steatohepatitis. Effects of HCQ were similar in those with negative anti-nuclear antibody (ANA) compared to those with weakly positive ANA (Figure A, B), suggesting that those are specific steatohepatitis-targeting rather than autoimmune-targeting effects from HCQ.

Thus, we aim to clarify whether HCQ relieves nonalcoholic steatohepatitis by reviewing medical records from our out-patient-clinic patients who accept the treatment of hydroxychloroquine (Plaquenil®).

A

B

Design : Retrospective study

Review medical records from patients who accept the treatment of hydroxychloroquine (Plaquenil®), find those with nonalcoholic steatohepatitis and observe the effects of hydroxychloroquine on them.

Methods :

Step 1 : screen out our targeted group : patients with nonalcoholic steatohepatitis

1. We have made a request to Information Technology Office of National Taiwan University Hospital, and this request is about the list of our out-patient-clinic patients who accept the treatment of hydroxychloroquine.
2. Collect and review the medical records, ultrasound and blood tests of patients in the abovementioned list and screen out those with nonalcoholic steatohepatitis based on the following criteria.

Inclusion criteria :

Our patients who taking hydroxychloroquine and match the following criteria

- A. Patients with fatty liver, based on the abdominal ultrasound report of which the date is the closest to the initial date of using HCQ.
- B. ALT level of 2.5 and 0.5 month prior to hydroxychloroquine treatment > 41 U/L
- C. With ALT result which is tested in 3 months after using HCQ.
- D. The initial date of taking HCQ is prior to September, 26, 2022, which is the date we got the list from Information Technology Office of National Taiwan University Hospital.

Exclusion criteria :

Our exclusion criteria can be separated into loose exclusion criteria and strict exclusion criteria.

Loose exclusion criteria : patients who match the following criteria will be excluded from the above group.

- A. Diseases of the biliary tract : the abdominal ultrasound report indicated the patient with stones in the biliary tract, or the patient with jaundice or his total bilirubin > 2.0 mg/dl
- B. Viral hepatitis : HBV Viral Load + or HCV Viral Load +
- C. Alcoholic steatohepatitis : History of drinking alcohol or AST/ALT > 1.5 and GGT > 2X
- D. Autoimmune hepatitis : ANA 1:80+ (above) or AMA+ anti-LKM+ or anti-SMA+
- E. Wilson's disease : ceruloplasmin < 20 mg/dl

Strict exclusion criteria : patients who had ever had viral hepatitis or was being infected by virus (HBV, HCV infection : HBsAg+ or anti-HBc+ or anti-HCV Ab+) will be further excluded from the above group.

The definition of months : used in the criteria evaluation and the data analysis

Before patients used HCQ :

- 0.5 month : During the periods from one month prior to the date of initial use of HCQ to that date, we define the date which is the closest to 0.5 month as -0.5 month.
- 2.5 months : During the periods from four months to one month prior to the date of initial use of HCQ, we define the date which is the closest to 2.5 months as -2.5 months.
- 5.5 months : During the periods from seven months to four months prior to the date of initial use of HCQ, we define the date which is the closest to 5.5 months as -5.5 months.

After patients used HCQ :

- 0.75 months : During the periods that patients used HCQ for 0-1.5 months, we define the date which is the closest to 0.75 months as 0.75 months.
- 3 months : During the periods that patients used HCQ for 1.5-4.5 months, we define the date which is the closest to 3 months as 3 months.
- 6 months : During the periods that patients used HCQ for 4.5-7.5 months, we define the date which is the closest to 6 months as 6 months.
- 9 months : During the periods that patients used HCQ for 7.5-10.5 months, we define the date which is the closest to 9 months as 9 months.
- 12 months : During the periods that patients used HCQ for 10.5-13.5 months, we define the date which is the closest to 9 months as 12 months.

Then, in addition to the above-mentioned criteria, we will record the following two things separately.

The first one is hemochromatosis. Hemochromatosis may also cause hepatitis, but the prevalence of this disease in Taiwan is very low. Thus, we do not list hemochromatosis in the exclusion criteria.

The second one is drug-induced hepatitis. We do not list suspected drug-induced hepatitis in the exclusion criteria since drug-induced hepatitis may not be accurately confirmed based on our current medical records. However, if we find patients using drugs which may be related to hepatitis, we will record their information separately, including the duration of using these drugs and the ALT levels after stopping using it.

Step 2 : collect and analyze patients' medical information

(These patients are those with NASH and accept the treatment of HCQ)

We plan to collect the following information of each patients

1. The date when each patient started to take HCQ
2. Birth date :
To realize how old the patients were when they started to take HCQ.
3. Gender
4. Historical blood test results :
 - A. ALT, AST, GGT, α -fetoprotein, platelet, FIB-4, WBC, bilirubin, albumin
 - a. For recording baseline demographics
 - b. To assess and analyze the status of hepatitis and liver fibrosis in each patient.
→ We plan to observe the ALT levels prior to the initial use of HCQ and ALT levels after it, and we will further analyze whether the ALT levels were decreased after patients took HCQ.
 - B. HbA1c*
 - a. For recording baseline demographics
 - b. To assess whether patients have diabetes mellitus
 - C. TG, TCHO*
 - a. For recording baseline demographics
 - b. To assess whether patients have hyperlipidemia

* We need these tests to realize whether patients have these comorbidities, since these are the risk factors of NASH.

Statistical Analysis Plan

1. We plan to use the statistical function of excel and Prism to analyze our results.
2. Initially, we will make the tables about the baseline demographics of patient who in our study group (patients with NASH and accept the treatment of HCQ), which we may use excel to help us arrange and analyze the tables.

- Then, we will check each patient's ALT levels in different month (prior to or after the initial use of HCQ), and we will use the date of initial use of HCQ as day0 and make box plots and violin plots to show the change of ALT levels with times going. We plan to use Prism to make the plots and analyze whether ALT levels were significantly decreased after patients took HCQ.

Members of our team

Position in this study	Name	Organizational Affiliation
Study Director	[name]	Graduate Institute of Pharmacology, College of Medicine, National Taiwan University
Study Principal Investigator	[name]., Ph.D.	1. Graduate Institute of Pharmacology, College of Medicine, National Taiwan University 2. Department of Internal Medicine, National Taiwan University Hospital

	Name	Organizational Affiliation	Phone and E-mail
Central Contact Person	[name]	Graduate Institute of Pharmacology, College of Medicine, National Taiwan University	[contact] E-mail : [contact]

References

- Pouwels, S., et al., *Non-alcoholic fatty liver disease (NAFLD): a review of pathophysiology, clinical management and effects of weight loss*. BMC Endocr Disord, 2022. **22**(1): p. 63.
- Niture, S., et al., *Emerging Roles of Impaired Autophagy in Fatty Liver Disease and Hepatocellular Carcinoma*. Int J Hepatol, 2021. **2021**: p. 6675762.

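### Patients whose earlier enzyme falls prompted this review may also be in the cohort that tests for an ALT fall, and the plan does not mark them or report without them

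*Combined protocol and SAP*

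**What the plan says.** The Abstract first cites published clinical and animal data and a mechanism as grounds for trying HCQ. It then reports local experience: "HCQ has been anecdotally prescribed to patients with steatohepatitis in our clinic", and "almost all those with HCQ treatment had immediate reduction of their liver enzyme levels". Two subgroups had already been inspected: "Effects of HCQ were similar in those with negative anti-nuclear antibody (ANA) compared to those with weakly positive ANA (Figure A, B").

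The aim follows from this: "Thus, we aim to clarify whether HCQ relieves nonalcoholic steatohepatitis by reviewing medical records from our out-patient-clinic patients who accept the treatment of hydroxychloroquine". Under Methods, Step 1, the cohort comes from a hospital data request: "this request is about the list of our out-patient-clinic patients who accept the treatment of hydroxychloroquine". Inclusion criterion D limits entry at one end only: "The initial date of taking HCQ is prior to September, 26, 2022". Loose exclusion criterion D removes some patients on serology, "Autoimmune hepatitis : ANA 1:80+ (above) or AMA+ anti-LKM+ or anti-SMA"+, but no criterion refers to patients already observed.

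Step 2 and the Statistical Analysis Plan compare ALT before and after the start of HCQ, in all eligible patients and without a control group. They name software but no test, significance level or sample size. They do not mention reporting the Figure A/B patients separately.

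**The concern.** The earlier observation and the planned test share a clinic, a drug and a type of outcome. The earlier patients had steatohepatitis, took HCQ and had enzyme results before and after treatment, which is close to what inclusion criteria A to C select. As the plan stands, any of them who meet the criteria enter the test with outcomes that have already been seen and judged favourable.

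A study run because one group looked good, which then counts that group again, carries the group's chance variation into its result. Both the p-value and the size of the ALT fall lean towards an effect. A reader could not tell whether the distortion is trivial or serious, because the plan does not provide for stating the overlap.

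**Working it through.** The plan states no test, alpha, power or sample size, so there is no figure of its own to reproduce. The check has two parts: whether overlap can occur under the text, and how much it would matter.

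**Can overlap occur?**
- Source of the earlier patients: the investigators' clinic (Abstract).
- Source of the cohort: a list of the same clinic's HCQ patients (Methods, Step 1).
- Time limit: HCQ started before 26 September 2022, with no earliest date (inclusion criterion D).
- What could remove earlier patients: ANA at 1:80 or above may take out part of the weakly ANA-positive group but not the ANA-negative group. The ultrasound, double-ALT, biliary, viral and alcohol criteria may take out others.
- Analyses that separate those who remain: none.

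Overlap is therefore possible and likely, but its size cannot be found from the documents.

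**How much would it matter?** Assumptions, none of them in the documents:
- no true effect;
- a test with a nominal 2.5% chance of a significant fall (Z > 1.96);
- equal variance in all patients, so that the overlap share f is also the share of information;
- an earlier group that, taken alone, had reached Z1 > c, with c = 1.645 or 1.96.

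With Z2 for the other patients, the pooled statistic is

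Z = √f · Z1 + √(1 − f) · Z2,

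and the quantity needed is P(Z > 1.96 | Z1 > c), that is

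[1 / P(Z1 > c)] · ∫ from c to ∞ of φ(z) · {1 − Φ[(1.96 − √f · z) / √(1 − f)]} dz.

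Numerical integration gives:

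| Overlap f | c = 1.645 | c = 1.96 |
|---|---|---|
| 2% | 4.6% | 5.0% |
| 5% | 6.3% | 7.1% |
| 10% | 8.6% | 10.1% |
| 20% | 12.7% | 15.7% |
| 33% | 17.9% | 23.1% |
| 50% | 25.1% | 33.8% |

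The estimate shifts as well. The mean of Z1 given Z1 > c is φ(c) / P(Z1 > c): 0.103 / 0.05 = 2.06 for c = 1.645, and 0.0584 / 0.025 = 2.34 for c = 1.96. The pooled estimate is therefore displaced by √f times that. At f = 0.33 the displacement is 0.574 × 2.06 = 1.2 to 0.574 × 2.34 = 1.3 standard errors.

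**A second model.** Here a paired t-test is used at two-sided 5% with no true change, and the study is run only because at least 80% (lower figure) or 90% (upper figure) of the earlier patients had a fall. There were 40,000 simulated studies per setting.
- 100 patients, 5 of them earlier patients: 5.6% to 6.4%.
- 100 patients, 10 earlier: 7.4% to 9.6%.
- 40 patients, 10 earlier: 11.1% to 16.2%.
- 40 patients, 20 earlier: 33.8% to 56.3%.

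Leaving the earlier patients out returned the error to 4.8% to 5.2% in every setting. The models agree on direction and on the pattern: small at low overlap, large at a third or more.

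**What separating these patients does not cure.** Entry requires ALT above 41 U/L at both −2.5 and −0.5 months. Assume log-normal ALT (median 50 U/L, log SD 0.6), 40 patients, no drug effect and a within-patient correlation of 0.9 down to 0.5. A before-after t-test at two-sided 5% then rejects in about 8% to 32% of studies from regression to the mean alone.

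**Cost in precision.** The interval without the flagged patients is wider by a factor of 1 / √(1 − f): 1 / √0.67 = 1.22 at one third flagged, 1 / √0.5 = 1.41 at one half.

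**The case against.** The strongest reply is that the case rests on inference, and much of that reply stands.

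- A reader might infer that the earlier patients are in the cohort. No text says so. It follows only for those who meet the criteria, and several criteria may remove some.
- A reader might infer that the hypothesis itself came from the clinic's enzyme falls. The Abstract gives a different order: published data and mechanism led to prescribing, and the falls then prompted this review. What is shared is the decision to test and part of the data, not the origin of the idea.
- A reader might infer that responders were picked one by one. The Abstract describes nearly all of a treated group, which implies that some had no fall, and cohort entry needs an ALT result after HCQ but not a particular value. What remains is selection at the level of the study, which is what the calculation models.
- Overlap, Z threshold and alpha are all assumed. At 2% overlap the chance is only about 5%.

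Two objections to possible remedies also stand. A flag for every patient whose ALT had been seen in routine care could cover most of the cohort, since these are the clinic's own patients. At 80% flagged the interval would be 1 / √0.2 = 2.2 times as wide. And an unflagged result does not deserve the label confirmatory in an uncontrolled before-after review.

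That retrospective reviews commonly reuse clinic patients is no answer. The problem is that outcomes already found favourable would be pooled unmarked into a test of the same outcome.

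**Conclusion.** The point holds as a possible overlap that the plan neither counts nor separates. Its direction is known: pooling the Figure A/B patients unmarked favours an ALT fall in both the test and the estimate. Its size is not known. Against a nominal 2.5%, the illustrative chance of a significant fall with no true effect runs from about 5% at 2% overlap, through 6-7% at 5% and 9-10% at 10%, to 18-23% at 33% and 25-34% at 50%. This assumes that the earlier group had itself reached Z > 1.645 to 1.96.

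The documents do not support saying that the cohort certainly contains these patients, or that the error rate is inflated by a particular amount. Separating them deals with this bias only. The lack of a control group and regression to the mean remain. The change is worth making because it is cheap and because only the investigators can supply the count.

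**What to change.** 1. In Step 2, add one column that flags only the patients shown in Figure A/B, whom the investigators can identify. State how many of them are in the cohort.
2. In the Statistical Analysis Plan, state that the ALT before-after result will be reported both without the flagged patients and in all patients.
3. State that if the fall is not seen without the flagged patients, the conclusion is limited to hypothesis-generating.
4. Call neither result confirmatory, and give the reason: there is no control group, and entry on raised ALT leaves regression to the mean.

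The cost is one column, one results row and a wider interval in the unflagged set: about 1.22 times if one third are flagged, more if the overlap is larger. No patient is dropped from the report. If the overlap proves to be very small, stating the count largely settles the matter.

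### The Objective asks whether HCQ treats NASH, but a before-after ALT test in HCQ users alone cannot separate an HCQ effect from other causes of an ALT fall

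*Combined protocol and SAP*

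**What the plan says.** The Objective reads "To examine whether hydroxychloroquine can treat nonalcoholic steatohepatitis effectively". The closing paragraph of the background states the aim in the same causal terms: to find out whether HCQ relieves NASH.

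Everything after that concerns one group. The Design section takes the records of patients given HCQ, to "find those with nonalcoholic steatohepatitis and observe the effects of hydroxychloroquine on them". In Methods, Step 1, the data request to the hospital's IT office is described thus: "this request is about the list of our out-patient-clinic patients who accept the treatment of hydroxychloroquine". The Statistical Analysis Plan refers to "our study group (patients with NASH and accept the treatment of HCQ" and defines no other group. Step 2 says "we will further analyze whether the ALT levels were decreased after patients took HCQ", and the SAP says the team will "analyze whether ALT levels were significantly decreased after patients took HCQ".

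Three further provisions matter:
- Inclusion criterion B is "ALT level of 2.5 and 0.5 month prior to hydroxychloroquine treatment > 41 U/L", so entry depends on the outcome variable.
- A third pre-HCQ window is defined ("we define the date which is the closest to 5.5 months as -5.5 months"). It is not an entry condition, and no analysis is assigned to it beyond the plots of ALT over time.
- Suspected drug-induced hepatitis is not an exclusion. Use of such drugs, and ALT after stopping them, is only recorded separately.

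The Step 2 collection list does not include weight, diet, exercise or other metabolic treatment.

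**The concern.** A before-after test within treated patients estimates the total change over the interval. It equals the HCQ effect only if ALT would otherwise have stayed level. The plan offers nothing to support that assumption, and several of its features work against it. Patients enter because ALT was raised. Some may have a suspect drug stopped. Other care may change at the visit at which HCQ is started, and the data needed to adjust for that are not collected.

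At stake is the main sentence of the eventual report. A significant fall would answer the question of whether ALT was lower afterwards. It would not answer the question the Objective poses. The background already reads an uncontrolled enzyme fall in the same clinic as relief of steatohepatitis, so the same step could easily be taken with the study result.

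**Working it through.** **Inputs.** The documents state no N, significance level, SD or expected effect, so there is no planned figure to reproduce. Every input below is an assumption except the entry rule (ALT > 41 U/L at -2.5 and -0.5 months) and the time windows.

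**1. Effect of a fall not due to HCQ.** Let *f* be the proportional ALT fall from any cause other than HCQ, *s* the SD of within-patient change in ln ALT, and *n* the number of patients. With zero HCQ effect, a two-sided 5% one-sample t test on the change has noncentrality

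λ = -ln(1 - f) × √n / s,

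and the chance of a significant fall is P(T > t₀.₉₇₅,ₙ₋₁), where T is noncentral t with n - 1 degrees of freedom and noncentrality λ.

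Example: f = 0.10, n = 50. Then -ln(0.90) = 0.1054 and √50 = 7.071. For s = 0.4, λ = 1.863; for s = 0.5, λ = 1.490. The critical value is 2.010. The probabilities are 0.447 and 0.309.

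Chance of a significant fall with no HCQ effect (nominal 2.5%), range for s = 0.5 to 0.4:

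| Usual-care fall | n = 30 | n = 50 | n = 100 |
|---|---|---|---|
| 5% | 8-10% | 11-14% | 17-25% |
| 10% | 20-29% | 31-45% | 55-74% |
| 15% | 41-58% | 62-80% | 90-98% |

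**2. Effect of the entry rule alone.** ALT was simulated as log-normal with total log SD 0.5 and equal correlation between visits, keeping patients above 41 U/L at both entry windows, with no drift and no HCQ effect. The mean fall from -0.5 to +3 months ranges from 1.2% (population median 60 U/L, correlation 0.9) to 20% (median 30, correlation 0.5). A middle case (median 45, correlation 0.7) gives 6.7%, with a significant fall in 16%, 26% and 46% of samples at n = 30, 50 and 100.

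**3. What the -5.5 month window can show.** Take median 60 U/L, between-patient log SD 0.45, within-patient log SD 0.3 and the same entry rule. Geometric mean ALT at -5.5, -2.5, -0.5 and +3 months is then about:
- no drift: 75, 78, 78, 75 U/L, a rise into the entry windows and a return to the -5.5 month level;
- steady 10% fall per 3.5 months: 87, 82, 78, 67 U/L, a decline visible before HCQ.

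The window can therefore reveal regression to the mean or a steady earlier decline. It cannot reveal a change that starts together with HCQ, because by definition no such change appears before day 0.

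**The case against.** The strongest reply is that this is openly a retrospective review, that it requires two raised ALT values rather than one, and that it plots ALT over several pre-HCQ windows, so a reader could judge whether ALT was already falling. Much of this stands. Two raised values lessen regression to the mean, and step 3 shows that the -5.5 month value is informative. But that value is not required for entry, no analysis uses it, and it cannot detect care that changes on the day HCQ starts.

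The documents do not support four stronger readings that a reader might infer:
- *That the pre-HCQ series must look flat because of criterion B.* The criterion applies to two windows only; with the third included, the series is not flat in either case in step 3.
- *That a positive result is likely even if HCQ does nothing.* At n = 50 with a 10% fall the chance is 31-45%, below even odds, and neither the fall nor N is known.
- *That an untreated group would restore a valid error rate.* This follows only if the groups are comparable. Simulating two identical groups returns the nominal rate by construction and says nothing about confounding by indication.
- *That a suitable untreated list is readily available.* The criteria use ultrasound and laboratory records, so it is plausible, but the documents describe only the HCQ list and do not show that other outpatients had the same work-up.

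Nor has the plan yet drawn a conclusion from this analysis; what it states is an aim.

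**Conclusion.** The point holds as a mismatch between a causal Objective and a single-group before-after test. No section separates an HCQ effect from changes in care that begin with HCQ, from stopping a suspect drug, from natural course or from selection on ALT. This rests on the text alone and needs no numerical assumption.

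The size is illustrative. On the assumed inputs, the chance of a false significant fall at n = 50 runs from 11-14% to 62-80% as the usual-care fall goes from 5% to 15%, against a nominal 2.5%. These figures show that such a result can be common; they do not estimate the bias in this cohort. Because the mismatch affects what the study may conclude, the wording must change. Adding a comparator is a debatable design improvement, not a condition.

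**What to change.** **Required.** Reword the Objective, the aim at the end of the background and the planned inference in the Statistical Analysis Plan along these lines: *to describe the course of ALT before and after the start of HCQ; the cause of any change is not established*. This costs no data or patient contact. The downside is a weaker claim.

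**Optional, if the IT office can supply the records (an assumption).** Add non-HCQ outpatients who meet inclusion A, B and C, with timing counted from an index visit, and the same exclusions. Define the index visit in advance, for example the first visit at which the -2.5 and -0.5 month windows qualify. Compare 3-month ln ALT between groups, adjusted for pre-index ln ALT, age, sex, calendar year, HbA1c, TG and TCHO, and report the result as an association.

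This costs one further data request and chart review, and confounding by indication would remain. In the model of step 3, the SD of change is 0.409 and the residual SD after adjustment for the -0.5 month value is 0.381. Relative to the one-group interval, the width is then 0.381 × √2 / 0.409 = 1.32 with one control per patient, or 0.381 × √1.5 / 0.409 = 1.14 with two: about 32% or 14% wider.

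### Inclusion A lets an ultrasound taken on HCQ decide fatty-liver status, and two undated loose exclusions also permit on-HCQ values; anchor all three at or before HCQ start

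*Combined protocol and SAP*

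**What the plan says.** All the criteria at issue stand under Methods, Step 1.

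- **Inclusion A** establishes fatty liver "based on the abdominal ultrasound report of which the date is the closest to the initial date of using HCQ". It does not say that the scan must precede HCQ, and it sets no maximum interval.
- **Loose exclusion A**, besides biliary stones on ultrasound, excludes on this limb: "or the patient with jaundice or his total bilirubin > 2.0 mg/dl". No date is attached.
- **Loose exclusion C** (alcoholic steatohepatitis) reads "History of drinking alcohol or AST/ALT > 1.5 and GGT > 2X". The laboratory limb has no date.
- **Inclusion B**, by contrast, is dated before start: "ALT level of 2.5 and 0.5 month prior to hydroxychloroquine treatment > 41 U/L". **Inclusion C** is dated after it: "With ALT result which is tested in 3 months after using HCQ".
- **Strict exclusion** states lifetime scope where that is meant: "patients who had ever had viral hepatitis or was being infected by virus".
- **Step 1, item 2** gives the material to be screened, with no cut-off date for the records: "Collect and review the medical records, ultrasound and blood tests of patients in the abovementioned list".

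The month windows are introduced as "The definition of months : used in the criteria evaluation and the data analysis". They lie on both sides of HCQ start, and none is assigned to inclusion A or to loose exclusions A and C. Step 2 and the Statistical Analysis Plan make the fall in ALT after HCQ start the outcome.

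**The concern.** The study is retrospective, so records from before and after HCQ start are both in view when eligibility is decided. In a single-arm before/after comparison, eligibility should rest on what was known at start. If it can rest on a later finding, entry to the cohort may depend on how the patient did on treatment.

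The plan's own rationale makes this more than formal. The Abstract reports a prompt fall in liver enzymes on HCQ, and the title of reference 5, which the Abstract cites for experimental animals, says that HCQ improves hepatic steatosis. If that also happens in patients, a scan on HCQ could miss fatty liver that was present at start. The AST/ALT ratio has ALT, the outcome, as its denominator. On-HCQ jaundice or raised bilirubin could, in turn, remove patients who got worse.

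At stake are which patients enter the cohort and, for the two undated exclusions, whether two people screening the same records would reach the same list.

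**Working it through.** The plan gives no figure to reproduce here. The check has four parts.

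**1. Does any text fix the timing?**

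| Criterion | Timing stated |
|---|---|
| Inclusion A, ultrasound | closest to start, either side |
| Inclusion B, ALT > 41 U/L | -2.5 and -0.5 month |
| Inclusion C, ALT available | 3 months after start |
| Loose exclusion A, jaundice or bilirubin > 2.0 mg/dl | none |
| Loose exclusion C, AST/ALT > 1.5 and GGT > 2X | none |

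The month definitions do not settle the last two rows, because they run from 7 months before start to 13.5 months after it. Step 2 lists AST, GGT and bilirubin for baseline recording but does not limit eligibility to pre-start values.

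**2. What does the closest-date rule select?** The dates below are illustrative, in days from HCQ start.

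| Scans available | Closest (current rule) | Most recent on or before start |
|---|---|---|
| -60, +10 | +10 (on HCQ) | -60 |
| -30, +45 | -30 | -30 |
| -200, +90 | +90 (on HCQ) | -200 |

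The documents do not show how often an on-HCQ scan would be chosen. As an assumption only: if scans fall at random, with a rate after start *r* times the rate before, the closest scan is on HCQ with probability *r*/(1 + *r*). For *r* = 0.5, 1 and 2 this is 33%, 50% and 67%.

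**3. How does the AST/ALT limb move with ALT?** The limb needs AST > 1.5 × ALT. The 1.5 and the 41 U/L are the protocol's; the on-HCQ ALT values are illustrative.

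- At the inclusion B visits, ALT > 41, so AST must exceed 1.5 × 41 = 61.5 U/L.
- ALT 40: AST > 1.5 × 40 = 60 U/L.
- ALT 30: AST > 1.5 × 30 = 45 U/L.
- ALT 20: AST > 1.5 × 20 = 30 U/L.

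Example with assumed values: before start, ALT 80 and AST 80 give a ratio of 80/80 = 1.00, and the patient is kept. If ALT halves to 40 on HCQ, the limb is met when AST stays above 60. Since 60/80 = 0.75, that means AST has fallen by less than 25%. GGT > 2X is also required, and AST must come from the same date as ALT.

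**4. Which way would each route push the result?**

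- A scan that clears on HCQ removes an improver, if clearing goes with a fall in ALT. This works against showing benefit.
- A ratio raised by falling ALT removes an improver. This also works against showing benefit.
- Jaundice or bilirubin > 2.0 mg/dl appearing on HCQ removes a patient who worsened. This works in favour of HCQ.

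A net figure would need the cohort size, scan dates, and bilirubin, AST and GGT data, none of which the documents give.

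**The case against.** The case for leaving the text alone has four parts.

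**The scan rule is a choice, not an ambiguity.** Inclusion A picks one scan per patient, ties apart, and the scan nearest start is a reasonable proxy for status at start. A scan shortly after start may describe that status better than one from many months before. This stands. A reader might infer that two people applying inclusion A could build different cohorts; the text does not support that, and the point about reproducibility applies only to the two undated exclusions. What remains is that the rule, followed to the letter, admits on-treatment scans at any distance.

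**The exclusions probably mean status at start.** Each is headed by a competing diagnosis, and the strict criterion spells out lifetime history where it is wanted. This reading is plausible, and nothing shows that on-HCQ values are intended. But it is an inference, and a one-line date would settle it.

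**The ratio route is narrow.** A reader might infer from inclusion C that every patient is exposed to an on-HCQ ratio. Inclusion C guarantees only an on-HCQ ALT; it requires neither AST nor GGT after start, and the rule needs both. The route is open only where those were also measured.

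**No bias is shown.** A reader might infer that the plan is tilted towards HCQ. The documents do not support this: two of the three routes work against showing benefit, and none has a known frequency. But effects of unknown size and opposite sign cannot be assumed to cancel.

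**Conclusion.** The point holds as an avoidable weakness in selection, of modest severity. For inclusion A it follows from the wording: an ultrasound taken on HCQ can decide entry to a before/after ALT analysis. For jaundice/bilirubin and AST/ALT with GGT it is weaker: the text permits on-HCQ values without saying they are meant.

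The direction of any net bias is unknown and its size cannot be computed. The firm numbers are the AST thresholds, which rest on the protocol's 41 U/L and 1.5; the on-HCQ ALT values, the example patient, the scan dates and the scan-rate ratios are assumptions. The documents do not show that on-HCQ findings were used, that the cohort is wrong, or that the result favours HCQ. Biliary stones as an exclusion, drinking history, and the viral, autoimmune and ceruloplasmin criteria are outside this point, except for one question about the stone limb raised in the fix.

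**What to change.** 1. **Ultrasound.** In the main analysis, define fatty liver by the most recent ultrasound on or before HCQ start, and report the scan-to-start interval. A hard look-back limit is not needed and would drop patients. As a sensitivity analysis, apply the current closest-date rule, which brings in patients whose only or nearest scan is after start and shows fatty liver, and report how many patients' status differs between the two rules. State whether the stone limb of loose exclusion A, which refers to the ultrasound report, uses the same pre-start scan.
2. **Jaundice/bilirubin and AST/ALT with GGT.** Apply these to any finding dated on or before HCQ start, with AST and ALT from the same date. Do not limit them to the -2.5 and -0.5 month windows: those reach back only four months, so a patient with jaundice recorded at, say, month -5 would no longer be excluded. Keep patients whose jaundice or bilirubin above 2.0 mg/dl first appears after start in the analysis, and list them separately.
3. **Missing values.** Do not exclude on a limb whose pre-start value is missing, and report how many patients this concerns.

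The cost is one date rule for three criteria and a date check in records already under review. Patients with no pre-start scan leave the main set, and an older pre-start scan may describe status at start less well than one taken just after it. The sensitivity analysis covers both. If few patients change status between the two rules, the sponsor can say so; if many do, readers need to know.
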